### Intermediate endpoints

#### a) Patient activation, self-efficacy and social support

An important intermediate endpoint is Veteran self-efficacy and patient activation. We hypothesize that exposure to **Vet-COACH** will improve chronic disease outcomes and lead to greater patient activation. We will use the Patient Activation Measure (PAM), a brief previously validated 13-item scale that assesses patient's self-rated ability to take preventive actions, manage symptoms of medical problems, find and use appropriate medical care, and work with their health care providers to make decisions about their care. The PAM includes important constructs including self-efficacy and is not disease-specific. We will use the multi-dimensional scale of perceived social support to assess overall social support. *In addition, we will utilize a measure of community support for healthy lifestyles (the Chronic Illness Resources Survey—Brief Form).*

#### b) Self-management behaviors and patient-provider communication

Self-management behaviors will be measured with the following scales: The nutritional assessment of eating behavior will be a self-reported assessment "Starting the conversation", an eight-item validated, simplified food instrument designed for use in primary care and health-promotion settings. We will utilize a food frequency questionnaire (FFQ) developed by the Nutrition Assessment Shared Resource of the Fred Hutchinson Cancer Research Center to measure nutritional intake. The FFQ provides estimates for 30 nutrients and has acceptable accuracy and reliability. Intake of fruits and vegetables, fat, and fiber can be calculated based on published algorithms. Level of physical activity will be assessed using the International Physical Activity Questionnaire (IPAQ), a validated and reliable measure of physical activity. All participants will have an assessment of medication adherence using a standardized participant interview. In addition, yearly medication adherence will be calculated from the electronic pharmacy data (ReComp). Tobacco use will be assessed with standard questions from the Behavioral Risk Factor Surveillance Survey (BRFSS). *We will assess alcohol consumption using the Alcohol Use Disorders Identification Test (AUDIT-C), a 3-item screening test for heavy drinking and/or abuse. We will ask about utilization of stress management techniques and patient-provider communication using previously validated questionnaires (CAHPS ).*

**Table 4. Outcome Measures; measured at baseline and 12 months**

	Measurement domain	Measurement instrument
Primary outcome		
Blood pressure	Systolic blood pressure (SBP)	Standard protocols 
Secondary outcomes		
Cardiovascular risk	Framingham risk score (FRS)	FRS algorithms 
Individual Cardio-metabolic risks	Body Mass Index (BMI) Low density lipoprotein cholesterol (LDL-c)	Standard protocols for height and weight Laboratory data from CPRS if within 3 months of enrollment, otherwise drawn by study RN at enrollment

Health Care Utilization	Outpatient and ER visits, hospitalizations, pharmacy utilization	Administrative data and participant self-report for non-VA care
Health-related quality of life	Role limitations caused by physical health, emotional problems, physical functioning, and general health	SF-12 
Intermediate outcomes		
Patient activation, Self-efficacy	Self-rated ability to take preventive actions, manage symptoms of medical problems, find and use appropriate medical care, and work with their health care providers	Patient Activation Measure (PAM) 
Social Support	Domains of Social support	Multidimensional Scale of Perceived Social Support 
Self-management Behaviors – Measure of behavioral enactment	Physical activity Nutrition – eating behavior, food frequency Medication adherence  Tobacco use Alcohol use Stress Management	IPAQ  “Starting the conversation”  , FFQ  Voils, C. I. et al. Medication adherence questionnaire  ReCOMP  Medication Possession Ratio BRFSS  AUDIT-C  Utilization of stress management techniques 
Patient provider communication	Communication with physician and health care team	Consumer Assessment of Health Plans (CAHPS)-patient-provider communication 

### Specific Aim 3: Determine intervention costs

These costs will include all labor and materials (pamphlets, home BP monitors, etc.) used in the intervention. We will administer weekly time sheets for all study personnel to estimate the amount of time they spend in various activities, and attribute the cost of these activities to either intervention costs or trial-specific costs, which are excluded from the intervention cost.

### Covariate data

We will collect data on potential covariates that have been shown in previous studies to be associated with self-care and quality of life. We will use these covariates in our analysis to describe the patient population and to adjust for any differences across randomized groups. Demographic covariates include age, gender, household income, marital status, education, primary language and race/ethnicity (American Indian or Alaskan Native, Asian, Pacific Islander, black, white and their ethnicity as Hispanic or non-Hispanic). We will assess health literacy using a brief validated 3 - item screener. Depressive symptoms will be assessed using the PHQ-8.

### Measuring Intervention fidelity

*Fidelity will be assessed to a) identify areas of needed improvement for ongoing remediation for the peer coaches through review of audio recordings (Section C.4.2); b) provide qualitative description of fidelity and needed changes to peer coaches at least quarterly (Section C.4.2); and c) include in the quantitative models to determine relationship between fidelity and outcomes (Section C.7.3). We will develop a manual for implementation of the intervention, very similar to our manual for our diabetes self-management trial (Appendix 3 of attached IIR). This manual consists of required and optional educational modules and educational materials that will be provided to the participant for each topic. To assess if participants received the*

*scheduled phone calls, the total number of phone calls will be recorded for each participant. Prior to study initiation and on a quarterly basis, peer support counselors must demonstrate competence in delivering content with fidelity ( $\geq 80\%$  of components). We will require the peer health coaches to complete an encounter form for each intervention visit; which will consist of a checklist of required modules and if they were delivered. We have developed encounter forms for our current CHW study that will be adapted for the current study. The study coordinators will abstract participant records to assess whether each client received the interventions specified by protocols. Study staff (RA, study coordinators, or Co-I) will also directly review audio recordings of one call per quarter to assess intervention fidelity. Fidelity will be measured using an observation form, and feedback will be given to each Vet-Coach. Monthly control reports will ensure that each participant received the required components of the intervention.*

#### **Specific Aim 4: patient and provider interviews**

We will use theoretical purposive sampling to identify three groups of Veterans for semi-structured interviews: 1) individuals who demonstrate significant improvement in hypertension control, 2) individuals without significant improvement and 3) individuals who discontinued the intervention after 1 or 2 sessions. Veterans within all groups will be interviewed upon exit (< 3 weeks of last attendance) and Veterans in groups 1 and 2 will also be interviewed one year post program completion. *We anticipate that interviewing 15 to 20 Veterans in each group (n = 45-60).* Groups will be purposively sampled to include both male and female Veterans. Sample interview guides are provided in Appendix 4 of attached IIR (Follow-up interviews questions will follow the same format and be developed from the initial interview findings). These participants will be contacted regarding willingness to participate in a 30-45 minute telephone based interview that will be audio recorded. The first 10–15 minutes will be open ended and elicit overall description of the participants' satisfaction with the intervention and experience with the program. Follow up questions and prompts will focus on specific aspects of the intervention and barriers and facilitators. Interviews will be conducted in the clinic either before or after scheduled medical visits or over the telephone, based on participant preference.

*We will also interview a subset of PACT team members (including Vet-Coaches, PCPs, RN case managers, LPNs, and pharmacists) whose patients' were enrolled in the program.*

Because we want to determine potential barriers and facilitators to implementation from the provider and PACT team perspective, the interviews will focus on staff perceptions of how the intervention helped, how it could be improved, potential barriers they can identify in implementation, and what changes in implementation strategy could potentially improve uptake. Vet-Coaches and PACT team members will be asked to participate in voluntary qualitative interviews at the end of the study. They will be provided with an Information Statement detailing their subject rights and study activities they will be asked to participate in. Standard audio equipment will be used to record telephone-based interviews. At their exit interview, we will assess satisfaction with the program and offer opportunities to provide feedback. Although the exact number of subjects needed to generate meaningful qualitative results cannot be identified *a priori*, the main goals relate to developing deep case-oriented perspectives, selecting subjects with a range of characteristics and perspectives, and achieving saturation (meaning the point at which subsequent interviews fail to produce new findings) for overriding content themes. Even though the precise number of cases required to achieve thematic saturation cannot be predetermined, the clarity of the topic being studied, multiple interviews with participants over time, the use of focused research questions and researcher experience decrease the sample needed for meaningful findings. *We anticipate interviewing 18 - 24 providers and PACT team members will be sufficient for meaningful findings. We will use purposive sampling to include up*

to eight Vet-Coaches, 5 -7 PCPs, RN case managers, and LPNs, 3 staff Pharmacists, and 2 outpatient nutritionists.

### Barriers and facilitators to implementation

We will collect information on the barriers and facilitators of implementation. We include features in the study implementation to promote external validity such as inclusive enrollment criteria and using the minimum intervention needed for change (e.g. implementing with the minimum intensity we believe necessary for effectiveness). We will ascertain the degree of participation by eligible Veterans. We will use the following measures: (1) ability to contact potential participants (# reached/ # contact attempts); (2) study enrollment rate (#enrolled in study/ #eligible reached); (3) study participation rate (# with at least one follow-up home visit or participation in one project group activity/ # eligible reached); (4) program dropout rate (# discharged from program/ # participating in program); (5) study completion rate (# completing exit data collection/ # enrolled in study). The project manager will track feasibility by logging program costs, FTE used, space used, and logistical barriers encountered. Program staff will complete time study logs weekly during the first six months of the project and then for one week every quarter. The program manager will collect data on adaptability by logging changes in the research model protocols as the program is implemented. We will assess components that worked well or did not through participant satisfaction questions at the exit interview, and semi-annual discussions among project staff and investigators.

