### Study design overview:

We propose a randomized controlled trial to evaluate the effectiveness of **Vet-COACH**, a peer health coach program to control hypertension and reduce CVD risk among Veterans. The original program incorporated home visits by peer health coaches to deliver health education, counseling and goal setting support. Due to safety concerns and social distancing restrictions stemming from the COVID 19 pandemic, the program has transitioned to conducting all health coaching encounters, as well as enrollment and exit visits, via phone. This transition was implemented under IRB approval of the miscellaneous memo submitted at the beginning of the pandemic. These changes to conduct all health coaching encounters and exit surveys over the phone will be permanent for the remainder of the study. Our operations partners from NCP have developed extensive patient educational materials that will be used for the current study. We will train the peer health coaches to provide brief educational messages and link Veterans to existing clinical services at VHA, including their primary care PACT teams and community based programs. The main outcome will be a reduction in systolic blood pressure. Secondary outcomes are cardiovascular risk, as measured by the Framingham Risk Score (FRS), health care utilization and intermediate behavioral outcomes including patient activation, social support and health behaviors (e.g. diet and physical activity, medication adherence). *We will randomize a total of 200 individuals to the intervention group and 200 individuals to the control group.*

Our study design has limitations. Because of the nature of the intervention, we are unable to blind treatment assignment. The PI and [name] will provide overall supervision to the peer coaches. This model is necessary for program development. Because the intervention is being conducted at two sites, we are not proposing an economic evaluation to estimate cost-effectiveness, in part because such data would be of limited generalizability. Positive findings will lead to a larger multi-site trial that would include a cost-effectiveness analysis. These limitations are more than balanced by the strengths of this proposal. The proposed project is a prospective, randomized controlled trial that examines important outcomes with statistical power to detect clinically meaningful differences.

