**Follow-up calls for Intervention Group:**

The same peer health coach will make a total of 10 phone calls over the 12 month intervention period (Table 3), including 5 phone calls (to replace the previous home visits) plus 5 telephone follow up calls. We are basing the intervention frequency and number of visits on our previous work (1R18DK088072-01) and on frequencies noted in successful blood pressure trials. To increase generalizability of this model, we chose a minimal intervention necessary to review education topics and address important behaviors for all Veterans with hypertension. The peer health coach will support the participant in plan implementation at follow-up calls taking place 2, 4, 6 and 9 months after the initial call. Follow up telephone contacts are being used in our current study to maintain contact and support for participants.

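### The study participation rate still counts only home visits or group activities, so Veterans coached solely by phone are scored as non-participants

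*Protocol*

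**What the plan says.** The Protocol section *Barriers and facilitators to implementation* (within 5.5) lists five measures, introduced as a way to learn how far eligible Veterans take part. Three matter here:

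- Measure 2: "study enrollment rate (#enrolled in study/ #eligible reached".
- Measure 3: "study participation rate (# with at least one follow-up home visit or participation in one project group activity/ # eligible reached".
- Measure 4: "program dropout rate (# discharged from program/ # participating in program".

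On delivery, the *Study design overview* (5.1) says: "The original program incorporated home visits by peer health coaches to deliver health education, counseling and goal setting support". It then reports that, because of the pandemic, "the program has transitioned to conducting all health coaching encounters, as well as enrollment and exit visits, via phone", and adds: "These changes to conduct all health coaching encounters and exit surveys over the phone will be permanent for the remainder of the study". The section *Follow-up calls for Intervention Group* describes the coach contacts purely as calls, "including 5 phone calls (to replace the previous home visits) plus 5 telephone follow up calls".

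On allocation, the overview says: "We will randomize a total of 200 individuals to the intervention group and 200 individuals to the control group". The section on the control arm treats home visits as part of the intervention and gives controls usual care and a pamphlet.

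SAP section 4 dates enrolment from 2017 to 2021, and SAP section 6 plans comparisons before and during the pandemic. The SAP does not define or revise the participation rate.

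**The concern.** The numerator of measure 3 names a mode of contact that the trial no longer uses. Its alternative route, a project group activity, is not described anywhere in either document. Walking groups, grocery store tours and the MOVE programme appear only as community or VHA resources to which Veterans may be referred. The definition was evidently not updated when coaching moved to phone.

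Aim 4 asks about barriers and facilitators to adoption, and the hybrid type 1 design is meant to inform later implementation. A rate that falls because the delivery mode changed, and not because fewer Veterans took part, would mislead on that question. It would also make the two delivery periods impossible to compare.

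**Working it through.** The Protocol states no value or target for this rate, so there is no figure to reproduce. The check applies the definitions to the planned numbers.

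**Inputs**

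- Randomised: 400 in total, 200 per arm (*Study design overview*).
- R = eligible Veterans reached. Not given, so assumed through the enrolment rate 400/R.
- p = share of the 200 intervention participants who never had a follow-up home visit because their coaching was by phone. Not given; 0%, 25% and 50% are assumed.
- Group activities: none described, so taken as zero.

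**Step 1. A participant coached only by phone.** Home visits = 0 and group activities = 0. The numerator contribution is 0, whether that Veteran completes one call or all of them. A participant who had at least one follow-up home visit before the switch still counts.

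**Step 2. Ceiling from allocation.** Only the 200 intervention participants can have a coach home visit. With perfect uptake and p = 0:

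participation rate = 200/R; enrolment rate = 400/R; ratio = 200/400 = 0.50.

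| Assumed enrolment rate | R = 400/rate | Ceiling 200/R |
|---|---|---|
| 20% | 2,000 | 10% |
| 40% | 1,000 | 20% |
| 60% | 667 | 30% |
| 100% | 400 | 50% |

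**Step 3. Further loss from the outdated numerator.** Ceiling = 200 × (1 − p)/R = 0.50 × (1 − p) × enrolment rate.

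| Assumed p | Ceiling as fraction of enrolment rate | Example at 40% enrolment (R = 1,000) |
|---|---|---|
| 0% | 0.50 | 200/1,000 = 20% |
| 25% | 0.375 | 150/1,000 = 15% |
| 50% | 0.25 | 100/1,000 = 10% |

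Uptake is perfect in every row. The fall from 20% to 10% comes only from calls not being counted.

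**Step 4. After updating the numerator.** With calls counted, the ceiling returns to 0.50 of the enrolment rate for every p. The same count over the 200 randomised to the intervention has a ceiling of 200/200 = 100% in both periods.

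**Step 5. Measure 4.** If its participating count is the measure 3 numerator, phone-only participants are outside the dropout denominator, and that denominator is 0 for them as a group. If it means anyone receiving the programme, there is no problem. The Protocol does not say which.

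**The case against.** The strongest reply is that *home visit* is a leftover label with a stated phone equivalent. The follow-up section says which calls replaced the visits, and Table 3 keeps home visits in its title while listing only calls. Staff who hold a call count for every participant would probably count the calls. That is plausible, but the definition does not say so, and the planned dose analysis lists visits and phone calls as separate items. The ambiguity stands.

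A second reply is that receipt of coaching is captured elsewhere: call totals, encounter forms and monthly reports under *Measuring Intervention fidelity*, and the dose analysis. This is true. It limits the harm and makes the repair easy, but it does not correct the rate itself.

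A reader might also infer that the denominator is wrong because it includes Veterans who declined and those randomised to control. The documents do not support that. The stated purpose is participation among eligible Veterans, so counting decliners is what a reach measure does, and measure 2 shares the denominator. Replacing it would substitute a different quantity, uptake among those assigned. The cap of one half is a known consequence of 1:1 allocation that needs stating.

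Nor can one conclude that the dropout rate is invalid, since nothing ties its denominator to measure 3.

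**Conclusion.** The point holds for the numerator of measure 3. Applied as written, it scores participants coached only by phone as non-participants and lowers the attainable rate by the factor (1 − p). The documents do not give p, so the fractions 0.375 and 0.25 of the enrolment rate are illustrations. The zero for phone-only participants needs no assumed enrolment rate or p, but it does rest on there having been no project group activity. The cap of one half also assumes none, and that controls received no home visits.

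It would go too far to say that everyone active after the switch scores zero, because one earlier follow-up home visit is enough to count. It would also go too far to say that the trial will report almost no uptake. That depends on p and on how staff read the label.

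The measure is descriptive and carries no hypothesis, threshold or progression rule. The primary systolic blood pressure analysis, its error rate and its power are untouched. A clarification is worth making because both delivery modes fall within the trial.

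**What to change.** Amend *Barriers and facilitators to implementation* as follows:

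1. Define the numerator of measure 3 as participants with at least one completed follow-up coaching encounter, meaning a home visit or the phone call that replaced it. State whether the initial coaching contact and the separate telephone follow-up calls count, so that both periods are scored alike.
2. Report the measure separately for the home-visit and phone periods, with a rule for participants who had both.
3. Keep eligible Veterans reached as the denominator, and note that 1:1 allocation caps the rate at half the enrolment rate. Alongside it, report the same numerator over the number randomised to the intervention.
4. State that the participating count in measure 4 is the updated numerator, so that phone-only participants are in the dropout denominator.

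The cost is a few sentences. Call totals and encounter forms are already kept for each participant under *Measuring Intervention fidelity*, so no new data collection is needed.

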## 5.6 Data Analysis

- Provide sample size determination and analysis (include anticipated rate of screen failures, study discontinuations, lost to follow-up etc.).
- Describe how, where and by whom the data will be analyzed.

### Specific Aim 1

The primary outcomes are changes from baseline to one year in systolic blood pressure. We will test the primary hypothesis that among Veterans with poorly controlled hypertension and at least one other CVD risk, the **Vet-COACH** intervention targeting behavior change and disease self-management will decrease SBP by 4 mmHg compared to a usual care + education control group.

